7.2.5 Sponsor Investigator Responsibility for Reporting Adverse Events

All Adverse Events will be reported to regulatory authorities, IRB/IECs and investigators in accordance with all applicable global laws and regulations.

8.0 STATISTICAL ANALYSIS PLAN

The initial dose escalation will follow a standard 3+3 design, starting at dose level 1. The decision to escalate to the next dose level will be determined by the rate of dose-limiting toxicity (DLT) observed during Cycle 2, with a cycle length defined as 3 weeks. Up to 3 patients will be initially enrolled in a dose cohort, starting at dose level 1. If 1 of 3 patients were to experience DLT, 3 additional patients will be enrolled at same dose level. If 0 of 3 patients or 1 of 6 patients enrolled at a dose level were to experience DLT, enrollment to next dose level will be opened. If >1 of 3 patients or >1 of 6 patients enrolled at a dose level were to experience DLT, the maximum tolerated dose (MTD) will have been exceeded. Adverse events will be collected and described for the expansion cohorts. Enrollment to dose level 1 will be expanded to 6 patients if applicable, or enrollment to dose level -1 will be opened if dose level 1 were to exceed the MTD. The highest dose level at which 0 of 3 patients or 1 of 6 patients experience DLT will be declared the MTD. A minimum of 6 patients and maximum of 18 patients will be enrolled for each cohort (Arm A: Lead in Trametinib and Arm B: Lead in Pembrolizumab) in this dose escalation portion of the study.

Enrollment into Cohorts A and B are pre-planned in regards to sequence and timing. Arm A (lead in trametinib) will open 1st to dose escalation and will accrue 3 patients. Once 3 patients are accrued for Arm A, Arm B will open and accrue 3 patients. This is to ensure cohorts remain open for accrual given the 6-week DLT period; these cohorts will alternate in opening in this fashion until the MTD is achieved for both Arm A and Arm B. Once the MTD is achieved for both Arms A and B, Arm A will open to dose expansion at the MTD and complete accrual, followed by Arm B. If one Arm is delayed in opening additional dose levels due to toxicity, the alternate cohort may open at additional dose levels if approved by the Primary Investigator in consultation with Novartis and Merck.

The recommended dose expansion and recommended phase II dose (RP2D) will be determined by the overall assessment of the MTD and toxicities observed in the study.

All patients who receive a dose of pembrolizumab and trametinib will be analyzed for safety and efficacy. Subjects who discontinue from study participation prior to receiving the combination of trametinib and pembrolizumab will be replaced. Subjects in dose escalation who discontinue from study and are not evaluable for dose limiting toxicities will be replaced. Patients removed from study for unacceptable treatment related adverse event(s) will be followed until resolution or stabilization of all treatment related AEs to grade 2 or lower. However, they will not be replaced.

A group of 12 patients will be enrolled in each of the 2 expansion cohorts at the MTD. Patients will enroll into the next subsequent cohort upon completion of the previous cohort (Arm A then Arm B). A sequencing scheme will be considered as promising if at least 5 of 12 patients were to achieve a complete or partial response per RECIST 1.1. The decision rule is associated with 80% exact power with an exact alpha of 0.16 if the underlying response rate associated with a sequencing scheme were truly at least 50% compared to current expectation of 25% ORR with single agent pembrolizumab. A median PFS of 8 months in 12 patients per cohort will provide 81 power to detect a difference compared to historical PFS of about 4 months with single agent pembrolizumab with an alpha of 0.1 based on accrual time of 24 months and follow up of 12 months. A sequencing scheme will be recommended for further development based on a combination of promising efficacy (response rate, PFS) and favorable changes in the tumor immune microenvironment at rebiopsy, provided the safety and tolerability profiles are acceptable.

Assays will be performed at the SU2C Lung Cancer Dream Team Immune Monitoring Core, Yale University, The Broad Institute, UCSF and at UC Davis Comprehensive Cancer Center as part of the SU2C Dream Team Lung Cancer Collaboration. Next generation sequencing by the Broad Institute will perform whole exome DNA/RNA sequencing to confirm KRAS amino acid substitution and examine mutational load and other co-mutations of interest and well as changes in RNA expression of relevant gene in the tumor immune microenvironment. A subset analysis will explore clinical outcome by KRAS amino acid substitution (G12C vs. non-G12C). The immune correlative studies performed in baseline and repeat biopsy specimens include: (in order of priority) 1) IHC and IF to determine PD-L1 expression, MEK target inhibition 2) additional immunophenotyping, and functional assessment of tumor infiltrating immune cells 3) Luminex evaluation of local tumor cytokine / chemokine signatures. In blood, FACS for quantification, immunophenotyping, and functional assessment of PBMCs will also be performed.

Adverse events will be summarized descriptively by type and by severity, with number and relative frequency calculated for all non-zero occurrences. With 16 patients treated at the MTD for either regimen, we will have an at least an 81% chance of seeing one or more cases of any adverse event that occurs in 10% or more patients.

All molecular and immune correlates will be assessed in exploratory analyses. Due to the limited sample size and exploratory framework, any such analysis will be stated carefully as hypothesisgenerating with the reported p-values not adjusted for multiple comparisons. Standard descriptive and graphical methods will be used to summarize the baseline levels and post-treatment changes for comparison of the three MEKi and pembrolizumab sequencing schemes, which will allow us to examine whether observed patterns are consistent with hypothesized mechanisms. The quantitative immune studies will be compared using a t-test to further inform the decision. Multiplicity of testing will not be considered since this considered an exploratory analysis. Association with response rate will be summarized descriptively by presenting the mean, SD, and other characteristics of molecular and immune measures, stratified by response status. Associations of molecular and immune measures with PFS will be summarized descriptively by stratified Kaplan-Meier curves and, if numbers permit, by proportional hazards models with molecular and immune responses as predictors. If the MEKi and pembrolizumab combination were not found to have sufficient activity, the molecular and immune patterns may

help explain the lack of activity. If sufficient activity were observed, then the correlates will be compared between patients who experience an objective response and those who did not. Results of these correlative studies including biopsies at pre-treatment and week 1 on treatment will be analyzed in conjunction with the Battle-Immunotherapy trial (with its later biopsy correlative timepoints) to inform the optimal dosing and sequencing of pembrolizumab with trametinib.

Decisions for whether to pursue one of these strategies in a larger trial will incorporate ORR, toxicity and immune correlative endpoints in collaboration with the company sponsors and SU2C Dream Team. The primary considerations will be ORR and toxicity, with immune and genomic correlative studies used as supplementary criteria.

If only one arm meets safety criteria and preliminary efficacy criteria (ORR \geq 50% or a median PFS \geq 8 months), then that treatment will be considered for future study. Immune and genomic correlative studies will be examined for the potential to inform future study design for that arm.

If both arms A and B meet the safety criteria and preliminary efficacy criteria and give comparable response rates and toxicities, we will carry out two additional sets of analyses to inform the decision process of which treatment to pursue for further study. First, we will use regression models to assess whether one arm might have superior performance after accounting for key patient differences (PD-L1 status, KRAS amino acid substitution (G12C vs. non-G12C), smoking status). We will assess whether one arm has superior ORR, using logistic regression analysis to control for clinical covariates, and whether one arm has superior PFS, using proportional hazards models to control for clinical covariates. Second we Second, we will examine biomarkers that might shed light on the impact of the treatments. We will compare exploratory immune correlates (enhanced tumor immune microenvironment). The final decision will be based on best clinical judgment of all investigators.

We expect that the distribution of PD-L1 expression in Arm A and Arm B to be comparable. Based on the current indication for first line pembrolizumab in PD-L1 high (>50%) NSCLC, the majority of patients accrued into this second line trial will likely contain tumors with lower PD-L1 expression. At completion of Arm A we will review baseline characteristics and current clinical practice at that time to assess whether it is anticipated there would be a shift in biomarker distribution in Arm B.

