5.4 Definition of Dose Limiting Toxicities

All toxicities will be graded using National Cancer Institute (NCI) CTCAE Version 4.0. The occurrence of any of the following toxicities during the first two cycles (i.e. after completion of the lead in cycle and the first cycle where both pembrolizumab and trametinib are administered) will be considered a DLT, if judged by the Investigator to be possibly, probably or definitely related to study drug administration. The goal of the dose escalation portion of the study is to assess the safety of the combination after pembrolizumab or trametinib lead in, therefore, patients must have completed the lead in phase and also have received both trametinib and pembrolizumab concurrently to be evaluable for a DLT.

A DLT evaluable subject is defined as a subject who receives treatment for the 6 week dose-limiting toxicity (DLT) observation period and who receives at least 80% of all planned treatments. A subject who does not receive at least 80% of planned treatment due to AEs that are unrelated to study treatment will not be considered evaluable for DLTs and may be replaced as

needed during dose escalation or dose confirmation. More than 3 or 6 subjects may be enrolled to a given dose level if needed to replace subjects who are not evaluable for DLT or to ensure a thorough evaluation of a given dose level during the dose escalation part of the study. An event will be considered a dose-limiting toxicity (DLT) if it occurs during the first two cycles of treatment (first 6 weeks after initiating treatment) and meets at least one of the following criteria:

- Clinically significant hematologic toxicity (e.g. grade 4 neutropenia lasting more than 7 days or accompanied by neutropenic fever, or Grade 4 thrombocytopenia of any duration)
- Clinically significant Grade ≥3 non-hematologic toxicity that has not been previously identified for either pembrolizumab or dabrafenib/trametinib and cannot be controlled with routine supportive measures (e.g. anti-emetics)
- Clinically significant Grade ≥3 non-hematologic toxicities that are known to occur with either pembrolizumab or trametinib but that cannot be controlled using the recommended product-specific supportive measures (e.g. steroids for pembrolizumab -related immune toxicities)

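### Section 8.0 states an MTD rule and a DLT window that differ from Section 5.4, and the text contradicts itself on lead-in DLTs

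*Combined protocol and SAP*

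**What the plan says.** **MTD rule.** Section 8.0: "The highest dose level at which 0 of 3 patients or 1 of 6 patients experience DLT will be declared the MTD". The stopping condition there is "If >1 of 3 patients or >1 of 6 patients enrolled at a dose level were to experience DLT". The only enlargement to six that it names is at the lower level: "Enrollment to dose level 1 will be expanded to 6 patients if applicable". It then says that "Arm A will open to dose expansion at the MTD and complete accrual, followed by Arm B".

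Section 5.4 defines the MTD as the highest dose with at most 1 DLT in 6 patients. The last row of Table 15 applies that to dose level 2 by name and requires at least six patients at the RP2D. The text after the table again refers to six patients at dose level 2. Section 5.2.1.1 describes the MTD as a level where six patients were treated.

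**Window.** Section 8.0 bases escalation on "the rate of dose-limiting toxicity (DLT) observed during Cycle 2". Its next paragraph explains the alternating accrual of the arms: "This is to ensure cohorts remain open for accrual given the 6-week DLT period". Section 5.4 counts an event "if it occurs during the first two cycles of treatment (first 6 weeks after initiating treatment", and one of its DLT criteria refers specifically to Cycle 1.

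**Lead-in DLTs.** Section 5.4 says "patients must have completed the lead in phase and also have received both trametinib and pembrolizumab concurrently to be evaluable for a DLT". It also says that a patient who receives under 80% of planned treatment because of unrelated adverse events is not evaluable. Section 8.0 replaces patients who leave before the combination and escalation patients who are not evaluable. It does not replace those removed for unacceptable treatment-related adverse events. Section 5.9, on replacement, is marked not applicable.

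**The concern.** Safety and tolerability is the primary objective, and the MTD feeds the dose given to 12 expansion patients per arm. After 0 DLTs in 3 patients at dose level 2, Section 8.0 read literally declares the MTD, while Section 5.4 cannot do so until six have been treated. Section 10.5 requires a meeting or call after each cohort's DLT assessment, and that meeting needs one rule.

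The window matters most in Arm A, where Cycle 1 is the first exposure to trametinib. The escalation sentence, taken alone, leaves a DLT there out of the decision. If a patient who stops for a lead-in DLT were treated as non-evaluable and replaced, a toxicity event would drop out of the 3+3 count.

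**Working it through.** **1. The plan's own figures.** Enumerating every 3+3 path over dose levels −1, 1 and 2, starting at level 1, gives 6 to 18 patients per arm under either rule. This reproduces the range in Section 8.0, so the range does not distinguish the rules. What differs is how small a path can end in an MTD:

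- Literal Section 8.0: 0/3 at level 1, then 0/3 at level 2, declares level 2 on three patients, with 3 + 3 = 6 in the arm.
- Section 5.4: every path that declares an MTD uses at least 3 + 6 = 9. A path of 6 ends with no MTD.

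Section 1.0 plans 9 per escalation arm (9 + 9 + 24 = 42), which fits 3 + 6. Its stated maximum of 62 does not match its own parts: 18 + 18 + 24 = 60.

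**2. What Table 15 does after 0/3 at dose level 2.** The row for 0 out of 3 says only to move to the next level, and Table 3 has none above level 2. The last row does cover level 2, with at most 1 of 6 and at least six at the RP2D. The required end state is therefore given. The step that leads to it is not.

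**3. Chance that dose level 2 is accepted once opened.** Let p be the true DLT rate (assumed, since the documents give none), q0 = (1−p)³ and q1 = 3p(1−p)².

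- Literal Section 8.0 (0/3, or 1/3 then 0/3): q0 + q1·q0
- Section 5.4 (at most 1/6): q0·(q0 + q1) + q1·q0
- Difference: q0·(1 − q0 − q1)

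For p = 0.20, q0 = 0.512 and q1 = 0.384. The literal rule gives 0.512 + 0.384 × 0.512 = 0.709. Section 5.4 gives 0.512 × 0.896 + 0.197 = 0.655.

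| Assumed p | Section 8.0, literal | Section 5.4 | Gap (points) | Share of literal acceptances on 3 patients, 1/(1+q1) | 0/3 results that 3 more patients would overturn, 1−q0−q1 |
|---|---|---|---|---|---|
| 20% | 70.9% | 65.5% | 5.3 | 72% | 10% |
| 25% | 60.0% | 53.4% | 6.6 | 70% | 16% |
| 33% (1/3) | 42.8% | 35.1% | 7.7 | 69% | 26% |
| 40% | 30.9% | 23.3% | 7.6 | 70% | 35% |

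**4. Precision, with no assumed rate.** Exact one-sided 95% upper limits on the DLT rate:

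- 0/3: 1 − 0.05^(1/3) = 63%
- 0/6: 1 − 0.05^(1/6) = 39%
- 1/6: 58%

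**5. Window.** Cycle 2 is 3 of the 6 weeks in Section 5.4. The documents give no lead-in DLT rates, so no effect can be calculated. It may be small in Arm B, since Section 4.3.2 reports no DLTs with single-agent pembrolizumab.

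**6. Lead-in DLT that prevents the combination.**

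| Favours counting it | Points the other way |
|---|---|
| Section 5.4: listed toxicities in the first two cycles are DLTs | Section 5.4: lead-in must be completed and both drugs received to be evaluable |
| Section 5.4: the 80% rule excludes only shortfalls due to unrelated events | Section 8.0: patients who leave before the combination are replaced |
| Section 8.0: patients removed for related toxicity are not replaced | Section 8.0: non-evaluable escalation patients are replaced |

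**The case against.** The strongest reply is that the intended rule is plain. Sections 5.2.1.1 and 5.4 point to six, Table 15's last row says so for dose level 2, and the planned 9 per arm agrees. The Table 2 footnote assigns the RP2D to the expansion cohorts, and the RP2D needs at least six patients. It may be set below the MTD for later or non-DLT toxicity, and a meeting or call follows each cohort. All of this stands, and it limits the point. It does not remove the conflict. Sections 5.2 and 8.0 also place expansion at the MTD, and no sentence says which section governs.

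The numerical effect is modest, as the reply also notes. The gaps apply only once dose level 2 is opened, only if the literal SAP sentence is followed, and only at assumed rates. The 63% limit after 0/3 is not far from the 58% after 1/6, a result that Section 5.4 accepts.

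A reader might go further on three points, and the documents do not support it:

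- **That expansion patients will receive a dose cleared on three.** The text just cited shows otherwise.
- **That the SAP minimum of 6 per arm confirms a three-patient MTD.** Section 1.0 ties that minimum to early termination for unacceptable toxicity.
- **That lead-in DLTs are simply ignored.** Section 5.4 counts them, Section 8.0 itself cites a six-week period, and its stopping condition states no window. On patients who never reach the combination, the text is contradictory, leaning towards counting related toxicity.

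**Conclusion.** The inconsistency holds. Section 8.0 gives a decision rule for the primary safety question that differs from Section 5.4 on the number of patients behind an MTD and on the window that drives escalation. If the literal SAP rule were followed, dose level 2, once opened, would be accepted 5.3 to 7.7 points more often at assumed true DLT rates of 20% to 40%, with an upper limit of 63% instead of 39% after a clean result. These figures assume independent patients with a common DLT rate. The window effect is unquantified, and the lead-in question is a contradiction in the text with no measurable size.

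Because the intended rule can be recovered from Section 5.4, this is not a design flaw. It should be corrected, but it is not in the class of errors that the trial cannot proceed without fixing.

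**What to change.** - **Section 8.0, escalation and MTD.** State that escalation uses DLTs as defined in Section 5.4 over Cycles 1 and 2 (6 weeks), and that the MTD is the highest dose level with at most 1 DLT in 6 evaluable patients. State that after 0 of 3 at dose level 2, three more patients are enrolled there before it is declared the MTD.
- **Table 15, row for 0 out of 3.** Add the same step for dose level 2.
- **Lead-in DLTs.** Amend the evaluability sentence in Section 5.4 and the replacement sentences in Section 8.0 themselves, by adding the exception that a patient with a treatment-related DLT during the lead-in is evaluable, counts as a DLT and is not replaced. A separate new sentence would leave the conflicting ones in force.
- **Section 1.0.** Correct the maximum from 62 to 60.

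The cost is wording, plus up to 3 patients per arm at dose level 2 relative to the literal SAP rule. Those patients are already within the planned 9 per arm (3 + 6), so the planned 42 and the corrected maximum of 60 do not change.

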- 7. The initial tumor imaging will be performed within 30 days prior to the first dose of trial treatment. Scans performed as part of routine clinical management are acceptable for use as the screening scan if they are of diagnostic quality and performed within 30 days prior to the first dose of trial treatment. On-study imaging will be performed every 9 weeks (63 ±7 days) after the first dose of trial treatment or more frequently if clinically indicated. The timing for imaging studies should follow calendar days and should not be adjusted for delays in cycle starts or extension of pembrolizumab /trametinib cycle frequencies. The same imaging technique should be used in a subject throughout the trial. CT including the chest, abdomen and pelvis or PET-CT is required for the baseline assessment. Patients who discontinue for reasons other than progression will be followed by imaging every 9 weeks.
- 8. Pembrolizumab (MK-3475) can be administered for up to 2 years. For the dose escalation and expansion Cohort (Arm) A (concurrent trametinib and pembrolizumab (MK-3475) both drugs will be administered as outlined in this protocol starting with cycle #1. For cohort B. trametinib will be initiated with cycle #1 and pembrolizumab (MK-3475) will commence in combination with trametinib starting with cycle #2, for Cohort C pembrolizumab (MK-3475) will be given for cycle 1 with concurrent trametinib added on C2D1.
- 9. Tumor biopsy for immune and molecular biomarker analysis will be performed prior to Cycle 1 of treatment either on archival tissue or fresh biopsy (within 6 months—no intervening treatment). Repeat biopsy will be performed on cycle 1 D11-13 or within 2 days after the last dose of trametinib for Arm A) and an optional end of study biopsy (within 28 days after progression).
- 10.Correlative blood draws for immune correlates will be performed prior to cycle 1 (- 3 days), prior to cycle 4 (-3 days), prior to cycle 7 (-3 days) and at discontinuation visit (± 5 days). Correlative blood draws for plasma DNA/RNA will be performed at baseline (cycle 1, day 1 prior to dosing or prior during screening), prior to each cycle of treatment (prior to concurrent administration of trametinib and pembrolizumab), and at progression (± 5 days).
- 11. Ophthalmology Exam: Indirect fundoscopic examination, visual acuity (corrected), visual field examination, tonometry, and direct fundoscopy within 6 weeks prior to registration.

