7.1.4.5 Follow-up Visits

Subjects who discontinue trial treatment for a reason other than disease progression will move into the Follow-Up Phase and should be assessed every 9 weeks $(63 \pm 7 \text{ days})$ by radiologic imaging to monitor disease status. After 1 year, the imaging time point will occur every 9 weeks $(\pm 7 \text{ days})$. Every effort should be made to collect information regarding disease status until the start of new anti-neoplastic therapy, disease progression, death, or end of the study. Information regarding post-study anti-neoplastic treatment will be collected if new treatment is initiated.

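### The DLT text conflicts on a related toxicity that ends treatment in the lead-in; separately, the safety and efficacy set, read literally, leaves lead-in stoppers out although the whole sequence is judged

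*Combined protocol and SAP*

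**What the plan says.** In each arm one drug is given alone in Cycle 1 and the other joins at C2D1 (Section 5.2).

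**Replacement (Section 8.0).** The plan says: "Subjects who discontinue from study participation prior to receiving the combination of trametinib and pembrolizumab will be replaced". It adds: "Subjects in dose escalation who discontinue from study and are not evaluable for dose limiting toxicities will be replaced". For patients removed because of an unacceptable treatment-related adverse event, it then says: "However, they will not be replaced". Section 5.9, which is headed as the replacement strategy, is marked not applicable. Section 5.4 allows more than 3 or 6 patients at a level where non-evaluable ones need replacing.

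**DLT window and evaluability.** Section 5.4 counts related toxicities in the first two cycles, that is, six weeks from the start of treatment, and one of its criteria names Cycle 1. It also requires a completed lead-in and both drugs together before a patient is evaluable. Its 80% dosing rule, however, declares non-evaluable only those who miss doses because of unrelated events. Section 8.0 bases escalation on DLTs in Cycle 2, but explains the alternating enrolment of the arms thus: "This is to ensure cohorts remain open for accrual given the 6-week DLT period".

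**Analysis set (Section 8.0).** "All patients who receive a dose of pembrolizumab and trametinib will be analyzed for safety and efficacy". No all-treated set is defined. The response rule is: "A sequencing scheme will be considered as promising if at least 5 of 12 patients were to achieve a complete or partial response". The objectives in Sections 3.1 and 3.2 concern the sequencing schemes, lead-in included.

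**The concern.** The two issues share a cause, namely that the plan does not settle the position of a patient who stops in the lead-in, but they differ in weight.

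The first is a contradiction. If a related toxicity ends treatment in Cycle 1, one set of sentences makes it a DLT and another makes the patient non-evaluable and replaced. In a 3+3 a single patient can decide whether the next level opens.

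The second is a choice of population. The lead-in drug is what distinguishes the arms, so early losses are part of what is being compared, and they may differ by arm. A set limited to patients who reached both drugs does not show them. Leaving them out will usually raise the observed ORR, though not always.

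**Working it through.** **A. Status of a related toxicity that ends treatment in the lead-in**

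| Question | Text pointing to a counted DLT | Text pointing the other way |
|---|---|---|
| Window | 5.4: first two cycles, with one criterion naming Cycle 1; 8.0: six-week period | 8.0: DLTs in Cycle 2 |
| Evaluable? | 5.4: the 80% rule drops only patients with unrelated events | 5.4: lead-in completed and both drugs received |
| Replaced? | 8.0: not replaced after a related event | 8.0: replaced if stopping before the combination, or if not DLT-evaluable |

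Take three patients, one with such an event and two without a DLT. Under the left column Table 15 reads 1/3, so three more enter the same level. Under the right column the patient is replaced; if the replacement has no DLT, the table reads 0/3 and the next level opens.

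Illustration. Inputs: DLT risk 20% in Cycle 2 and q1 = 2, 5 or 10% in the lead-in. All are assumptions; the documents give no rates.
- Per-patient risk if lead-in events count: q = q1 + (1 − q1) × 0.20, which gives 0.216, 0.240 and 0.280.
- A level passes on 0/3, or on 1/3 followed by 0/3: (1 − q)³ + 3q(1 − q)⁵.
- q = 0.216: 0.482 + 0.192 = 0.674. q = 0.240: 0.439 + 0.183 = 0.622. q = 0.280: 0.373 + 0.163 = 0.536.
- If those patients are dropped and replaced, q = 0.20: 0.512 + 0.197 = 0.709.

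**B. The response rule**

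The plan's own figures come first. With X binomial (12, p), P(X ≥ 5) is 0.158 at p = 0.25 and 0.806 at p = 0.50. The stated alpha of 0.16 and power of 80% reproduce.

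Let d be the share stopping in the lead-in and s their response rate. The documents give neither, and do not say whether 25% and 50% refer to all starters or to patients given both drugs.

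If 25% is the rate among all starters, the rate in the both-drugs set is (0.25 − d·s)/(1 − d).

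| d | s | Both-drugs ORR | P(X ≥ 5 of 12) |
|---|---|---|---|
| 0 | – | 0.250 | 0.158 |
| 5% | 0 | 0.263 | 0.186 |
| 10% | 0 | 0.278 | 0.220 |
| 20% | 0 | 0.3125 | 0.310 |
| 10% | 10% | 0.267 | 0.194 |
| 10% | 25% | 0.250 | 0.158 |
| 10% | 28% | 0.247 | 0.151 |

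The 28% row uses the pembrolizumab response figure for KRAS-mutant tumours in Section 4.3.1. If 25% already refers to patients given both drugs, the probability stays at 0.158 whatever d is.

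Single cases: five responders among 12 analysed, with two replaced non-responding stoppers, is 5/12 = 42% as reported and 5/14 = 36% among starters. With one replaced stopper who responds, 5/12 = 42% becomes 6/13 = 46%.

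Effects on PFS and on the adverse-event tables were not quantified.

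**The case against.** **On DLTs.** One coherent reading exists: patients stopped by related toxicity remain evaluable and are not replaced, while other stoppers are replaced. The 80% rule and the no-replacement sentence both fit it. It does not remove the conflict, because Section 5.4 still demands a completed lead-in and Section 8.0 still names Cycle 2. A reader might go further and infer that such a patient is neither evaluable nor replaced, leaving Table 15 with two evaluable patients and no rule. The documents do not support that: Section 5.4 permits extra enrolment to replace non-evaluable patients, and its 80% rule does not drop those with related events. The entry in Section 5.9 is no help, but it is not a competing rule either.

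**On the analysis set.** Section 5.4 gives a reason for requiring both drugs, namely that escalation is about the combination after the lead-in, and Section 3.1 also speaks of the combination. That is a legitimate choice for a phase Ib trial. A reader might infer that lead-in adverse events go unreported. They do not: Section 7.2 collects all events from treatment allocation, Section 8.0 summarises adverse events without stating a both-drugs limit, and Section 10.5 brings serious events to the cohort meetings. Their absence from the tables is only an inference from the set definition and the replacement sentence.

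Nor are stoppers necessarily unobserved. Section 6.0 says: "Patients who discontinue for reasons other than progression will be followed by imaging every 9 weeks", and Section 7.1.4.5 agrees: "Subjects who discontinue trial treatment for a reason other than disease progression will move into the Follow-Up Phase". In practice the first scan is at week 9 and disease follow-up ends when new anticancer treatment starts, so some will have no response assessment. A high response rate among Arm A stoppers would also be surprising, since Section 4.3.1 regards MEK inhibition alone as insufficient.

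Finally, the response rule is not the sole criterion: Section 8.0 also weighs toxicity, PFS and the immune correlates.

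**Conclusion.** The DLT text is wrong as written, in that its statements on window, evaluability and replacement cannot all be applied to a related toxicity that ends treatment in the lead-in. This conclusion rests on the wording alone. Its size is illustrative: under the assumed risks, the chance that a level passes differs by 0.04 to 0.17 (0.709 against 0.674 down to 0.536).

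The analysis-set point is a cheap improvement, not an error in a stated figure. Alpha and power reproduce. The rise to 0.186–0.310 needs three assumptions: 5–20% stopping, no responses among stoppers, and 25% meaning all starters. It shrinks, vanishes or slightly reverses when these change.

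A reader might conclude that the 5-of-12 rule must move to the first 12 treated patients. The documents do not compel that, and it has a price. If 50% is meant for both-drug patients and stoppers do not respond, the rate among starters is 0.50 × (1 − d), and power falls from 0.806 to 0.754, 0.696 and 0.562 at 5, 10 and 20% stopping. Fewer of the 12 would also have had the combination.

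**What to change.** 1. **DLT text.** Reconcile Sections 5.4 (including Table 15), 5.9 and 8.0 on window, evaluability and replacement. Each patient who stops in the lead-in should have one defined status, and a DLT that qualifies in the reconciled window should not be lost from the count. Which window and evaluability rule to adopt is for the investigators. Cost: wording only.

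2. **Analysis sets.** Define the safety set as all patients who receive at least one dose of either drug. Keep the 5-of-12 rule on the both-drugs set. Beside it, report ORR and PFS from C1D1 in all treated patients, counting those with no post-baseline assessment as non-responders for ORR. Tabulate lead-in stops with reasons, by arm, and state which population the 25% and 50% rates refer to. Cost: a little more analysis, and an all-treated ORR that may look less favourable.
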